**NCT04702191**

**Statistical analysis plan: 3 April 2024**

## Introduction and trial design

Promoting Healthy Families is a three-arm trial undertaken in the province of Ontario, in which Triple P and Circle of Security Parenting Program (COSP) are compared against a treatment as usual (TAU) control in four community-based agencies. Randomisation was undertaken stratified by agency using a block size of 6. The trial included baseline, post-intervention, six-month and 12-month assessment points. Two further waves at three and nine months focused on service use.

This statistical analysis plan (SAP) is an addendum to the original protocol for the trial, and includes an updated account of measures used to capture psychosocial outcomes. Details of the statistical analysis plan largely mirror those in the original protocol, but in the event of any differences, the current SAP supersedes the protocol. Outcomes relating to health economic assessment (service use, quality of life), parenting observations and psychophysiological assessments are not included in the SAP and will be addressed in future addenda.

## Outcomes and baseline characteristics

**Outcome measures.** Outcomes in this trial are reflected below in Table 1. The primary outcomes for this trial are the Strengths and Difficulties Questionnaire (SDQ) total problem score, and the Overreactivity subscale of the Parenting Scale. An additional primary outcome relating to observed parenting is not addressed in this SAP. Additional outcomes are broadly grouped into parenting capacity, child outcomes and other parental outcomes. Of note is that at each assessment point, the SDQ was administered in an age-appropriate form (aged 2-3 years, aged 4 and above). Scores are interchangeable between forms of the SDQ and thus these were ‘stacked’ for analysis.

In the original trial protocol, the data analysis plan included Parenting Daily Hassles and Plotkin Child Vignettes. Due to issues with data collection, Parenting Daily Hassles data were not considered to be reliable and thus we dropped this outcome from the analysis plan. Plotkin Child Vignettes data were not collected due to the need to minimise time and frequency of home visits during COVID-19 lockdowns.

**Baseline characteristics.** A number of baseline family characteristics are also relevant to this analysis. These include:

- Child age at baseline
- Parental education (beyond high school vs not)
- Family income (moderate poverty vs no poverty)
- Family structure (single-parent vs other)

We will also consider total child behaviour problems (SDQ total problems score) and parental distress (CESD-10) as relevant baseline characteristics. We will include these baseline characteristics in relevant imputation and effect modification models.

**Table 1. Outcome measures**

Measure	Variable	BL	PT	6-mo	12-mo	Analysis strategy
Primary Outcomes						
Strengths and Difficulties Questionnaire (SDQ; 2-4 years; 4-18 years)	Child behavioural problems	X	X	X	X	Sum score
Overreactivity Scale	Parental harsh discipline	X	X	X	X	Sum score
Additional Outcomes						
Parenting capacity						
Composite Caregiving Questionnaire	Self-efficacy Empathy Helplessness Reflective function	X	X	X	X	Subscale scores
Difficulties in Emotion Regulation Scale (DERS-SF)	Emotion regulation	X		X	X	Sum score
Parent Cognition Scale	Parental attributions	X	X	X	X	Sum score
Laxness Scale	Dysfunctional discipline	X	X	X	X	Sum score
Brief Child Abuse Potential Inventory	Child abuse risk	X	X	X	X	Sum score
Child outcomes						
Parent-Child Conflict-Tactics Scale-Revised (CTSPC-R)	Parenting practices				X	Sum score
SDQ Prosocial Behaviour Subscale	Child prosocial behaviour	X	X	X	X	Sum score (of subscale)
Other parental outcomes						
Alcohol Use Disorders Identification Test Consumption (AUDIT-C)	Parental alcohol and substance use	X		X	X	Scale score (complex scoring)
Cannabis use	Parental alcohol and substance use	X		X	X	Single item
Center for Epidemiologic Studies Depression Scale (CESD-10)	Parental mental health	X	X	X	X	Sum score
Generalized Anxiety Disorder (GAD-7)	Parental mental health	X	X	X	X	Sum score

Marital Conflict Questionnaire	Partner conflict	X	X	X	X	Sum score
Dyadic Adjustment Scale (DAS-7)	Partner conflict	X	X	X	X	Sum score
Exploratory outcomes						
SDQ problem behaviour subscales	Child behavioural problems	X	X	X	X	Subscale scores
Other outcomes not in this SAP						
Child and Adolescent Service Use Schedule (CA-SUS)	Health service utilization (children)	X		X	X	
HUI3 proxy parental report and Health Status Classification System Preschool Version	Health-related quality of life (children)	X		X	X	
HUI3	Health-related quality of life (adult)	X		X	X	
Emotional Availability Scale (EAS)	Observed parenting (parental sensitivity)	X	X	X	X	
EAS (child scales)	Responsiveness	X	X	X	X	

BL, baseline; PT, post-treatment

## Analysis principles

We will analyse this phase III effectiveness trial using the intention-to-treat principle in a superiority framework. We will use frequentist methods and a nominal significance level of 0.05 for two-sided tests. In all analyses, the primary comparisons will be Triple P vs TAU and COSP vs TAU. To control for false discovery, we will implement a Bonferroni correction within each primary outcome analysis used to conclude effectiveness (i.e. using  $p=0.025$  for each pairwise comparison vs TAU). We will not use a Bonferroni correction for additional outcomes. All effect estimates will be accompanied by 95% confidence intervals.

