Both the Marital Conflict Questionnaire and DAS-7 pertain only to people who reported being partnered at a given assessment point. We will assess any changes in eligibility for these measures over assessment points and use conditional imputation to account for these variables. In addition, because CTSPC-R was only administered to a subset of participants for whom home visits were possible, we will not include CTSPC-R in any imputation models.

**Effect estimation.** The general framework for effect estimation will be generalised linear mixed-effects models, with measurements (level 1) nested within families (level 2). The general form of each model is to include terms at level 1 for categorical time and for the interaction of intervention by categorical time, and at level 2 for study site as the stratification factor. This is equivalent to a model where the baseline measure is constrained to be equal between groups. Consistent with guidance from Coffman et al. (2016), we will not include a level 2 intervention term as this is essentially uninterpretable in the context of randomisation.

For each outcome model, we will select an appropriate outcome distribution, preferring an identity link where possible. If necessary to accommodate distributional violations, we will use percentile-based confidence intervals, undertaking cluster-level bootstrapping within each imputation and pooling runs to generate confidence intervals. In situations where variables have a limited range and discrete values, we will consider use of an ordered logit model. We will use Rubin's rules to combine estimates from multiple imputations.

The test of effectiveness will focus on the six-month value of the outcome. Correspondingly, we will examine the intervention-by-time interaction for the six-month assessment point for each intervention, and undertake a Wald test for each interaction (or, if bootstrapped models are used, examine a 97.5% confidence interval).

**Sensitivity analysis.** We will re-estimate all outcome models using unimputed data.

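### Is a fixed 0.025 for each comparison with TAU a flaw, given that Holm's procedure would reject at least as often within each primary outcome?

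*SAP*

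**What the plan says.** Under Analysis principles the SAP sets "a nominal significance level of 0.05 for two-sided tests" and states that "the primary comparisons will be Triple P vs TAU and COSP vs TAU". It then says that "we will implement a Bonferroni correction within each primary outcome analysis used to conclude effectiveness", with 0.025 for each comparison. The purpose it gives is control of false discovery. It states no numerical familywise target, and it describes no correction across primary outcomes.

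Under Effect estimation (Analysis strategy) the six-month intervention-by-time interaction is the confirmatory quantity. The SAP will "undertake a Wald test for each interaction (or, if bootstrapped models are used, examine a 97.5% confidence interval".

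For reporting, "All effect estimates will be accompanied by 95% confidence intervals".

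On the outcomes: "The primary outcomes for this trial are the Strengths and Difficulties Questionnaire (SDQ) total problem score, and the Overreactivity subscale of the Parenting Scale". There is one more: "An additional primary outcome relating to observed parenting is not addressed in this SAP".

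**The concern.** Bonferroni is not the most powerful way to protect two tests. Holm compares the smaller p-value with 0.025 and, only if that is significant, the larger with 0.05. It rejects everything Bonferroni rejects and sometimes more, with familywise error within the outcome still at most 5% under any dependence.

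Suppose one programme has p = 0.01 and the other p = 0.04 on the same primary outcome. The SAP does not declare the second effective; Holm would. In a trial that tests two programmes separately against TAU, showing that both work is a result worth having, so the rule appears to give away power for nothing.

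The reporting rule adds to this impression. A 95% interval that excludes zero can stand beside a negative verdict at 0.025.

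**Working it through.** **Inputs.** From the SAP: two-sided 0.05, two comparisons per primary outcome, 0.025 each, and a 97.5% interval if models are bootstrapped. The SAP gives no power, effect size, sample size or allocation ratio, so the following are assumptions:
- Equal allocation to the three arms. The block size ("Randomisation was undertaken stratified by agency using a block size of 6") is compatible with this, since 6/3 = 2 per arm, but does not fix it. With a shared control the two contrasts then correlate at about 0.5.
- 80% power at 0.025 for a programme that works.

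**1. The SAP's own figure.** 0.05/2 = 0.025, as stated. The matching two-sided interval is 1 − 0.025 = 97.5%, also as stated. The Wald route and the bootstrap route agree.

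**2. Validity.** The bound is 2 × 0.025 = 0.05. The actual familywise error for one outcome when neither programme works is:

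| Correlation of contrasts | Familywise error |
|---|---|
| 0 | 1 − 0.975² = 4.94% |
| 0.3 | 4.84% |
| 0.5 | 4.65% |
| 0.7 | 4.30% |

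Holm gives the same values in this case, because its first step is the same test.

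**3. What Holm would gain.** The critical values are 2.2414 (0.025) and 1.9600 (0.05). At 80% power the noncentrality is 2.2414 + 0.8416 = 3.0830. Holm's power for a comparison is

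P(|Z1| > 2.2414) + P(1.9600 < |Z1| ≤ 2.2414 and |Z2| > 2.2414).

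With equal effects and correlation 0.5:
- Per comparison: 0.8000 + 0.0456 = 0.8456.
- At least one: 0.8000 + 0.8000 − 0.6872 = 0.9128 under both rules.
- Both: 0.6872 under Bonferroni; 0.6872 + 2 × 0.0456 = 0.7784 under Holm.

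If the second programme's effect is half that of the first, the stronger programme goes from 80.0% to 80.6% and the weaker from 24.2% to 32.9%. If the second has no effect, the effective programme goes from 80.0% to 80.2%.

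**4. What Holm would cost.** Suppose one programme works (80% power) and the other does not. The ineffective programme's false-positive chance on that outcome is 2.5% under the SAP. Under Holm it is 4.24%, approaching 5% as the other effect grows. If one programme works on every primary outcome and the other on none, the ineffective programme's chance of at least one false positive, with uncorrelated outcomes, is:

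| Primary outcomes | SAP rule | Holm |
|---|---|---|
| 2 (in this SAP) | 1 − 0.975² = 4.9% | 1 − 0.9576² = 8.3% |
| 3 (if observed parenting used the same rule) | 1 − 0.975³ = 7.3% | 1 − 0.9576³ = 12.2% |

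In simulation with a between-outcome correlation of 0.9, the figures are 3.6% against 6.0% for two outcomes and 4.4% against 7.2% for three.

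**5. The 95% intervals.** These are for reporting; the decision is tied to 0.025 or the 97.5% interval, so the two statements do not contradict each other. Holm would not remove the mismatch either. With p = 0.03 and p = 0.04 both 95% intervals exclude zero and neither rule declares an effect. With equal effects, the chance of at least one such mismatch falls from 13.1% to 4.0%; with one real effect it falls only from 9.3% to 7.4%.

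**The case for a change.** The best case for a change is that Holm's advantage needs no assumption about power or correlation. Within one outcome it never rejects less than Bonferroni and keeps the same 5% bound, and it would take one sentence and one clause to adopt. The SAP says it supersedes the protocol where they differ, so it is the natural place to fix the rule. The limit on false positives across outcomes that Holm loosens is a by-product, not something the SAP promises.

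The mathematics of this stands, and so does the example of p = 0.01 and p = 0.04. Three parts of the argument do not carry over to a criticism of the SAP:
- The 5% familywise target within an outcome is a natural reading, but the SAP does not state it. A fixed 2.5% per programme per outcome fits the text equally well, and on that reading Holm weakens the protection.
- The change is not free. Two 97.5% intervals have joint coverage of at least 1 − 2 × 0.025 = 95% and give the same verdicts as the tests. Under Holm the interval level that decides one programme depends on the other's result, and that simple correspondence is lost.
- The SAP is dated 3 April 2024 and describes randomisation and the assessments in the past tense. Loosening a success rule at that stage is defensible only if results by arm are still unseen, which a reader cannot check from this document.

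**Conclusion.** The concern does not hold. The SAP's correction is valid, correctly calculated, completely specified and consistent between Analysis principles and Effect estimation. That a more powerful valid procedure exists does not make a standard one badly fixed.

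The choice is a trade-off that a trial team may settle either way. Holm offers nothing on the chance of at least one success (91.3% under both rules) and about 9 percentage points on showing both effective (77.8 − 68.7 = 9.1). The price is a false-positive chance for an ineffective programme that rises by about 1.7 points per outcome (4.2 − 2.5), in a plan with several primary outcomes and no described correction across them. Keeping the present rule is reasonable.

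The power and false-positive figures rest on assumed equal allocation, contrast correlation of 0.5 and 80% power. The SAP rule's 5% bound within each outcome, and its agreement with the 97.5% interval, rest on none of these.

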## Analysis strategy

**Descriptive statistics.** We will describe each study arm using means, standard deviations, proportions and quantiles with respect to key demographics for parents and children.

**Missing data.** It is unlikely that our analysis will accrue more than 10% missingness for any one outcome. However, to ensure that subsets of data can be used in later analyses, we will implement a multiple imputation strategy across all outcomes.

First, we will inspect individual scale responses at each assessment point will be inspected. In situations where participants have answered 75% or more of scales (or subscales where these are analysed separately) scored using simple sums, we will sum the available items and ‘upweight’ these to match the same possible range as for the full scale. This strategy is based on the generally high reliability and validity established for all study measures in this analysis, and is a conservative version of the rule originally proposed by Graham (2012). Where scales do not use simple sums (specifically, AUDIT-C), we will reserve individual items for imputation.

Second, we will specify an imputation model using fully conditional specifications. All scale variables will be analysed using predictive mean matching with five donors. Where items are imputed for AUDIT-C and cannabis use, we will use a conditional imputation model to account for the logic of these items’ scoring and an ordered logit link. We will include as auxiliary variables all relevant baseline characteristics identified above, as well as the site-specific stratum variable. We will undertake 10 imputations separately for each trial arm.

It is likely that the number of variables to be included will be too large for one imputation model. If a single imputation model fails due to nonconvergence or multicollinearity, we will undertake three imputation models using the same set of auxiliary variables in each one:

- SDQ problem subscales (primary outcome) and prosocial behaviour subscale;
- Overreactivity (primary outcome) and parenting capacity outcomes; and
- other parental outcomes.

Both the Marital Conflict Questionnaire and DAS-7 pertain only to people who reported being partnered at a given assessment point. We will assess any changes in eligibility for these measures over assessment points and use conditional imputation to account for these variables. In addition, because CTSPC-R was only administered to a subset of participants for whom home visits were possible, we will not include CTSPC-R in any imputation models.

**Effect estimation.** The general framework for effect estimation will be generalised linear mixed-effects models, with measurements (level 1) nested within families (level 2). The general form of each model is to include terms at level 1 for categorical time and for the interaction of intervention by categorical time, and at level 2 for study site as the stratification factor. This is equivalent to a model where the baseline measure is constrained to be equal between groups. Consistent with guidance from Coffman et al. (2016), we will not include a level 2 intervention term as this is essentially uninterpretable in the context of randomisation.

For each outcome model, we will select an appropriate outcome distribution, preferring an identity link where possible. If necessary to accommodate distributional violations, we will use percentile-based confidence intervals, undertaking cluster-level bootstrapping within each imputation and pooling runs to generate confidence intervals. In situations where variables have a limited range and discrete values, we will consider use of an ordered logit model. We will use Rubin's rules to combine estimates from multiple imputations.

The test of effectiveness will focus on the six-month value of the outcome. Correspondingly, we will examine the intervention-by-time interaction for the six-month assessment point for each intervention, and undertake a Wald test for each interaction (or, if bootstrapped models are used, examine a 97.5% confidence interval).

**Sensitivity analysis.** We will re-estimate all outcome models using unimputed data.

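### The by-arm imputation model has no measure of programme exposure, so the intention-to-treat effect may be modestly overstated if families who stop benefit less and are lost more often

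*SAP*

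**What the plan says.** Under Analysis principles the SAP commits to analysis "using the intention-to-treat principle in a superiority framework". Under Analysis strategy, Missing data, it states that "we will implement a multiple imputation strategy across all outcomes", using fully conditional specification with predictive mean matching for scale scores. On the expected amount of missing data: "It is unlikely that our analysis will accrue more than 10% missingness for any one outcome".

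On what enters the model beyond the outcomes: "We will include as auxiliary variables all relevant baseline characteristics identified above, as well as the site-specific stratum variable". Outcomes and baseline characteristics lists child age, parental education, income, family structure, baseline SDQ total and baseline CESD-10, and adds: "We will include these baseline characteristics in relevant imputation and effect modification models". On the pool of donors: "We will undertake 10 imputations separately for each trial arm".

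If one model cannot be fitted, three smaller models replace it, with the same auxiliaries in each. The sole sensitivity analysis refits the outcome models without imputation. Attendance, dose and completion appear in none of the imputation model, the outcome model or the sensitivity analysis. The Introduction says the SAP takes precedence where it differs from the protocol.

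**The concern.** Intention-to-treat needs the outcomes of all families as randomised, including those who stopped the programme. Because imputation is done within arm, a missing Triple P or COSP family takes values from observed families in the same arm. A family with no follow-up score can be matched only on baseline values and site. If stopping is linked both to less benefit and to loss from the study, attenders are over-represented among the donors. The missing stoppers are then credited with benefit that they did not have.

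At stake are the six-month contrasts with TAU on the two primary outcomes, and the other imputed contrasts. The comparison of Triple P with COSP would also be affected if stopping differs between them. The unimputed re-analysis also ignores programme status and relies on a similar missing-at-random assumption, so the two analyses could agree and share the same bias.

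**Working it through.** The SAP states no attendance rate, effect size or bias figure, so there is nothing of its own to reproduce. The only input it supplies is the 10% expectation for missing data. The rest are assumptions.

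**Inputs**
- *m*, share of an active arm missing at six months: 10% (the SAP's figure, which is per outcome and not per arm).
- *q*, share stopping the programme: 30% (assumed).
- *s*, share of the missing who had stopped: 50% to 100% (assumed).
- *r*, share of the attenders' benefit that stoppers keep: 0 or 0.5 (assumed).
- The TAU mean is taken as unbiased (assumed).

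**Formulas**, with the attenders' effect set to 1, for missing families who have no follow-up score:
- True intention-to-treat effect = (1 − q) + q·r
- Effect after imputation blind to stopping = [(1 − q − (1 − s)m) + (q − s·m)r] / (1 − m)

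| s | r | True | Imputed | Ratio |
|---|---|---|---|---|
| 1 | 0 | 0.70 | 0.70/0.90 = 0.778 | 1.111 |
| 0.75 | 0 | 0.70 | 0.675/0.90 = 0.750 | 1.071 |
| 1 | 0.5 | 0.85 | 0.80/0.90 = 0.889 | 1.046 |
| 0.5 | 0 | 0.70 | 0.65/0.90 = 0.722 | 1.032 |
| 0.5 | 0.5 | 0.85 | 0.775/0.90 = 0.861 | 1.013 |

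With s = 1 and r = 0 the ratio reduces to 1/(1 − m): 1.053 at 5% missing, 1.111 at 10%, and 1.25 at 20%, which is beyond what the SAP expects. If attenders gain an assumed 0.4 SD, the 10% worst case is 0.4 × 0.778 = 0.311 SD against 0.4 × 0.70 = 0.28 SD, an excess of 0.031 SD.

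**Effect of later scores.** The auxiliary list is not the whole model, because both primary outcomes are also measured post-treatment and at 12 months (Table 1). A simulation of 2,000,000 families in one active arm (assumed effect 0.3 SD, regression imputation standing in for predictive mean matching) used the baseline score and, where observed, the post-treatment score. It did not use the 12-month score. Ratios at m = 10%, q = 30%:

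| Post-treatment score in the missing families | s = 1, r = 0 | s = 0.75, r = 0 | s = 0.75, r = 0.5 |
|---|---|---|---|
| Missing for all | 1.109 | 1.071 | 1.029 |
| Missing for half | 1.087 | 1.055 | 1.022 |
| Observed for all | 1.062 | 1.039 | 1.017 |

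**When the bias vanishes or reverses.** With no programme effect the simulated estimate was 0.000. With r = 1 there was no bias. With r = 1.3 (stoppers respond better; s = 1, post-treatment score missing) the ratio was 0.979, an understatement.

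**With a stopping indicator in the imputation model** the ratio was 0.998 to 1.002 in every scenario of the simulation grid, which covered 10% and 20% missing.

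**The case against.** A reader might infer that the intention-to-treat effect is overstated in every contrast with TAU. The SAP does not support that. It would require that stoppers lose benefit, that they are over-represented among the missing, and that observed scores do not already carry the loss. The document has no data on any of these.

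A reader might also infer that the missing are imputed almost wholly from completers. That is not established either. Stoppers who stay in follow-up are donors too: in the worst case above they are 0.20/0.90 = 22% of the observed arm, against 30% as randomised.

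Other points stand in part:
- Within-arm imputation under missing-at-random does not contradict intention-to-treat, and no sentence of the SAP is wrong here.
- The SAP does not say what TAU contains, and under Additional analyses it notes that TAU varies by site. Families may be able to leave TAU services too, so it is assumed that the error does not cancel between arms.
- The size is small at the missingness the SAP expects, and the mechanism creates no false effect when the programme has none.
- The protocol is not at hand and may cover attendance.

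These points limit the claim but do not remove the gap. The SAP specifies the imputation model itself, and neither that model nor its sensitivity analysis takes account of programme status. The fallback models keep each outcome's own later scores but separate the outcome domains, so fewer follow-up scores can stand in for exposure. The emotion-regulation scale, AUDIT-C and cannabis use have no post-treatment measure of their own (Table 1).

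**Conclusion.** The point holds conditionally. The imputation model omits programme exposure. If stoppers benefit less and are lost more often, the intention-to-treat effect may be overstated by about 1-9% at 10% missing in an active arm. The ceiling is about 11%, when all the missing are stoppers with no benefit and no post-treatment score. An observed post-treatment score for all the missing lowers that worst case to about 6%, and a 12-month score would be expected to reduce it further.

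These sizes rest on assumed stopping rates, benefit and correlations, and on an unbiased TAU mean. Prognostic differences between missing and observed families, which could act either way in any arm, were not modelled. The 10% is also not a per-arm limit. With equal arms, 15% missing in each programme and none in TAU still averages (15 + 15 + 0)/3 = 10%, and the worst case becomes 1/(1 − 0.15) = 1.18. The gap is worth closing because doing so is cheap. It does not show that the trial's result is biased.

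**What to change.** In the SAP, Analysis strategy, Missing data, after the sentence on auxiliary variables, add that the Triple P and COSP imputation models will also include the number of sessions attended, or a completion indicator if only that was recorded. State that this applies to the single model and to each of the three fallback models. Leave it out of the TAU model, where this exposure is not defined. Keep the outcome model unchanged, so that the estimand stays intention-to-treat. Report six-month missingness by arm and, in the active arms, by completion status, so that readers can judge whether the issue matters.

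The cost is a sentence or two in the SAP, one more variable in two of the three by-arm runs, and one descriptive table. It depends on the four agencies having recorded attendance, which is an assumption because the SAP does not mention it. If few stoppers were assessed at six months, intervals will widen and the same donors will be reused. If none were, the term cannot be estimated, and a delta-adjusted sensitivity analysis of the six-month primary outcomes is needed instead.

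### If the three-block fallback imputation feeds the mediation analyses, mediator-outcome paths that cross blocks shrink toward zero under dropout

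*SAP*

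**What the plan says.** Under Missing data, the SAP first plans one imputation model, then warns: "It is likely that the number of variables to be included will be too large for one imputation model". If that model fails through nonconvergence or multicollinearity, the fallback is: "we will undertake three imputation models using the same set of auxiliary variables in each one". Block 1 is "SDQ problem subscales (primary outcome) and prosocial behaviour subscale". Block 2 is Overreactivity with the parenting-capacity outcomes, and block 3 is the other parental outcomes, including the CESD-10. The auxiliaries common to all three are site and the baseline characteristics, among them baseline SDQ total and baseline CESD-10 ("We will include these baseline characteristics in relevant imputation and effect modification models"). Imputation is by arm, using predictive mean matching with five donors and 10 imputations.

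On the amount of missing data: "It is unlikely that our analysis will accrue more than 10% missingness for any one outcome". On the purpose of imputing: "to ensure that subsets of data can be used in later analyses, we will implement a multiple imputation strategy across all outcomes".

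Mediation analyses (under Additional analyses) pair a mediator showing an effect at six months with an outcome showing an effect at 12 months, where a plausible relationship exists. The model adjusts for site and for the baseline mediator and outcome. The section does not say whether imputed or unimputed data are used. The only check on imputation is under Sensitivity analysis: "We will re-estimate all outcome models using unimputed data".

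**The concern.** An imputation model should contain the associations that the later analysis estimates. Under the fallback, a missing 12-month SDQ score is drawn without the six-month parenting or CESD-10 score, and a missing six-month mediator is drawn without any follow-up SDQ score. For a parenting programme, parenting to child behaviour is an obvious candidate pathway, and it crosses blocks 1 and 2.

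In imputed rows, the mediator-outcome association survives only as far as it runs through other waves of the same measure, the shared baseline scales and arm. The rest is lost, and the estimated path shrinks. The planned sensitivity analysis is worded for outcome models and does not mention mediation, so nothing in the plan is stated to reveal this.

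**Working it through.** **Inputs.** From the SAP: the block membership, auxiliaries, by-arm imputation, time points and mediation covariates given above, and 10% as the level of missingness it does not expect to exceed. The SAP states no bias, correlation or sample size for this point, so there is no figure to reproduce. Correlations, dropout timing and arm size below are assumptions. Data are taken as missing completely at random.

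**1. Formula.** Let b be the coefficient of the six-month mediator (M6) on the 12-month outcome (Y12), given arm and both baselines. Let a fraction p of rows have Y12 imputed, and let r be the share of b that survives in those rows. With M6 observed, the pooled coefficient in large samples is b(1 - p) + b·r·p, so

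relative bias = -p(1 - r).

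The same form holds when a family loses all follow-up, because the imputed M6 keeps its distribution given baseline.

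**2. Two limits at p = 0.10.**
- *All dropout before first follow-up, CESD-10 as mediator, SDQ as outcome.* Both baselines are in both blocks. Given these, the two imputed values are independent draws, so r = 0 and the bias is -0.10 × (1 - 0) = -10%.
- *All dropout at 12 months.* Y12 is imputed from earlier SDQ waves, which carry part of the association. Over the assumed structures, bias ran from -0.5% (r = 1 - 0.5/10 = 0.95) to -9.2% (r = 1 - 9.2/10 = 0.08).

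**3. Range over assumed structures.** For each missingness pattern, missing values are drawn from their own block. Pattern covariances are mixed by their probabilities, and the slope is compared with the complete-data slope. Set A has 1,614 structures (wave-to-wave stability 0.5-0.85, concurrent mediator-SDQ correlation 0.2-0.5, lagged-to-concurrent ratio 0.5-1.0). Set B has 729 cross-lag structures. Set C has 1,449 (autoregression 0.3-0.7, lagged path 0.05-0.3, concurrent residual correlation 0-0.6). Sets D and E have 432 and 91. Bias in the path (%) at 10% missing:

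| Pattern | A | B | C | D | E |
|---|---|---|---|---|---|
| Gradual dropout | -7.9 to -2.2 | -9.6 to -6.2 | -9.8 to -2.5 | -9.5 to -3.0 | -7.8 to -1.6 |
| All before first follow-up | -11.0 to -4.4 | -10.0 | about -10 | -10 | -10.0 |
| All at 12 months | not run | not run | -9.2 to -0.5 | -8.8 to -0.8 | not run |
| Whole-wave intermittent gaps | -11.1 to +6.8 | -13.7 to -0.3 | -16.4 to +3.7 | none upward | -10.8 to +9.1 |

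The gradual row for C spans cumulative timings of 1/3/10%, 3/6/10% and 6/8/10%. For D it spans two timings. No dropout case was upward in any set. For intermittent gaps, 29% of structures were upward in A, 3% in C and none in B or D. In A, upward bias came mainly with a low lagged-to-concurrent ratio: 92% of structures at 0.5, about 1% at 0.9-1.0.

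**4. Less missing data.** At 5% missing, gradual dropout gives -3.9% to -1.1% in A and -4.9% to -2.6% in C.

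**5. Dependence on covariates.** The table uses the covariates the SAP lists. If the six-month outcome were also adjusted for, set C gives about -10% to -32% for gradual dropout and about -21% to +86% for intermittent gaps.

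**6. Check with the planned method.** Five-donor predictive mean matching by arm, with 30,000 per arm and three structures from A, gave -3.6%, -5.9% and -6.8% under dropout, against -3.6%, -5.8% and -7.0% from the exact calculation. Imputing the pair jointly left -0.2% to +0.6%, over dropout and whole-wave gaps together. With an assumed 100 per arm and 10 imputations, split blocks gave -7.8% (dropout) and -10.3% (scattered scale gaps), and joint imputation -1.3% and -1.7%.

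**7. Consequence.** The arm-to-mediator path is little affected, since each measure is imputed by arm from its own waves. The indirect effect therefore shrinks by about the same percentage as b. For the b path alone, with its standard error held fixed, 80% power means z = 1.960 + 0.842 = 2.802:
- 3% loss: 2.802 × 0.97 - 1.960 = 0.758, power 77.6%
- 6% loss: 2.802 × 0.94 - 1.960 = 0.674, power 75.0%
- 10% loss: 2.802 × 0.90 - 1.960 = 0.562, power 71.3%

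For a borderline path at z = 2, a 6% loss is 2 × 0.06 = 0.12 of a standard error.

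**The case against.** Three conditions must coincide: the single model fails, mediation uses imputed data, and a cross-block pair passes all three mediation criteria. The SAP settles none of them. Mediation is an additional analysis meant to explore pathways, and 0.12 of a standard error will rarely change a reading. Splitting by domain is a sensible prespecified response to an oversized model, softened by the shared baseline SDQ and CESD-10 and by imputing within arm. The calculations treat the SDQ as one score, whereas block 1 holds subscales, and every correlation is assumed. The power figures concern one path with its standard error fixed, not the bootstrapped indirect effect. All of this stands, and it keeps the point minor. It does not remove the mechanism: no dropout case tried was free of shrinkage.

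Some stronger readings are tempting but unsupported:
- *That the loss is at least 2%.* With dropout concentrated at 12 months it fell below 1%.
- *That intermittent gaps typically inflate the path.* Upward cases depend on the assumed structure and were a minority or absent wherever they were counted.
- *That the SAP commits mediation to imputed data.* The reference to later analyses suggests it, but mediation is not named.
- *That the effectiveness results are biased.* Each primary outcome is imputed by arm with its own waves, so the six-month tests are little affected.

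**Conclusion.** The concern holds conditionally and is minor. If the fallback is used and mediation runs on those data, cross-block mediator-outcome paths are biased toward zero under dropout. At 10% missing the shrinkage is about 1% to 10%, near the top when families leave early and near the bottom when they leave late and earlier outcome waves carry the association. At 5% missing it is about half. Intermittent gaps mostly shrink the path too, with a sign that depends on structure.

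These figures rest on assumed correlations, data missing completely at random, and the covariates the SAP lists. The SAP calls the mediation model fully longitudinal. If that means also adjusting for the six-month outcome, the shrinkage under dropout would be larger. Within-block mediation is little affected.

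**What to change.** Add two or three sentences to the SAP:

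1. State which data the mediation analyses use.
2. If the fallback is used and mediation uses imputed data, then for each cross-block pair meeting the mediation criteria, impute mediator and outcome at all waves in one model, with the same auxiliaries and by arm. Keep the conditional imputation already set for AUDIT-C, cannabis use and the partner measures.
3. Repeat the mediation on unimputed data. This is free of the cross-block bias if data are missing completely at random.

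The SAP already allows, for outcome models, "undertaking cluster-level bootstrapping within each imputation and pooling runs to generate confidence intervals". The same device could serve the bootstrapped indirect effects.

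The cost is one extra imputation run per eligible pair. For most scales this holds 4 + 4 = 8 wave-scores (4 + 3 = 7 with DERS-SF) plus auxiliaries. By Table 1, block 2 holds 4 + 16 + 3 + 4 + 4 + 4 = 35, so size should rarely be a problem. A pair involving AUDIT-C needs more work because its items are imputed.

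There are two downsides. Total effects in a mediation model may differ slightly from the main estimates, because the imputed sets differ. In small samples with intermittent gaps the gain is not uniform: in one structure, with an assumed 100 per arm and 4 imputations, pair imputation left -2.9% against +1.7% for split blocks (Monte Carlo standard error 0.5).
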